7.1.2 Serious Adverse Event (SAE)

Serious Adverse Event (SAE) means any untoward medical occurrence that results in any of the following outcomes:

- Death. Results in death.
- Life-threatening. Is life-threatening (refers to an AE in which the patient was at risk of death at the time of the event. It does not refer to an event which hypothetically might have caused death if it were more severe).
- Hospitalization. Requires inpatient hospitalization or prolongation of an existing hospitalization.
- Disability/incapacity. Results in persistent or significant disability or incapacity. (Disability is defined as a substantial disruption of a person's ability to conduct normal life functions).
- Pregnancy.
- Medically important event. This refers to an AE that may not result in death, be immediately life threatening, or require hospitalization, but may be considered serious when, based on appropriate medical judgment, may jeopardize the patient, require medical or surgical intervention to prevent one of the outcomes listed above, or involves suspected transmission via a medicinal product of an infectious agent. Examples of such medical events include allergic bronchospasm requiring intensive treatment in an emergency room or at home, blood dyscrasias or convulsions that do not result in inpatient hospitalization, or the development of drug dependency or drug abuse; any organism, virus, or infectious particle (e.g., prion protein transmitting transmissible spongiform encephalopathy), pathogenic or nonpathogenic, is considered an infectious agent.

7.1.3 Attribution of an Adverse Event

An assessment of the relationship between the adverse event and the medical intervention, using the following categories:

Definitely Related: The AE is clearly related to the intervention. There is clear evidence to suggest a causal relationship, and other possible contributing factors can be ruled out.

Probably Related: The AE is likely related to the intervention. There is evidence to suggest a causal relationship, and the influence of other factors is unlikely.

Possibly Related: The AE may be related to the intervention. There is some evidence to suggest a causal relationship (e.g., the event occurred within a reasonable time after administration of the trial medication). However, the influence of other factors may have contributed to the event (e.g., the subject's clinical condition, other concomitant events).

Unlikely: The AE is doubtfully related to the intervention. A clinical event, including an abnormal laboratory test result, whose temporal relationship to drug administration makes a causal relationship improbable (e.g., the event did not occur within a reasonable time after administration

Version Date: 10/31/2022

of the trial medication) and in which other drugs or chemicals or underlying disease provides plausible explanations (e.g., the subject's clinical condition, other concomitant treatments).

Unrelated: The AE is clearly NOT related to the intervention. The AE is completely independent of study drug administration, and/or evidence exists that the event is definitely related to another etiology.

7.1.4 Expectedness of an Adverse Event

Study investigator or treating physician will be responsible for determining whether an AE is expected or unexpected, as indicated in the protocol, informed consent form and/or drug information brochure. An AE will be considered unexpected if the nature, severity, or frequency of the event is NOT consistent with the risk information previously described for the study intervention.

7.2 Collection and Reporting Requirements for Adverse Events and Serious Adverse **Events**

Only grade 3,4 and 5 adverse events (including SAEs) must be recorded in OnCore[®] and/or an adverse event log. All AEs required to be collected must be graded according to the CTCAE v5. When possible, signs and symptoms indicating a common underlying pathology should be noted as one comprehensive event. Investigator's or treating physician's assessment of AE attributions must also be documented.

AEs will be collected from the time the subject signs the consent form through 30 days post last dose of study drug(s). AEs will be tracked and followed until resolution, subject withdraws consent, or is lost to follow-up (including subjects who discontinue early). All adverse events collected per the protocol will be followed with appropriate medical management until they are resolved, if they are related to the study treatment, or until the investigator deems the event to be chronic. Please see section 7.2.2 and Table 1 to identify the adverse events that need to be reported.

7.2.1 Reporting of Adverse Events and Serious Adverse Events

Please refer to Table 1 below to identify adverse events that meet reporting requirements.

All serious adverse events (SAEs) that occur after the subject has signed the consent form through 30 days post last dose of study drug(s) will be reported. All SAEs will be followed until satisfactory resolution, or until the investigator deems the event to be chronic. All serious adverse events (SAEs) must also be documented in OnCore®.

Table 1

	SAE			AE			
Attribution	Grade 1, 2 & 3		Grade 4 and 5		Grade 3	Gr	ade 4
	Expected	Unexpected	Expected	Unexpected	Unexpected	Expected	Unexpected

MCW Protocol No: PRO00035737 39 Version No. 7

Unrelated Unlikely	IRB ¹ and DSMC ² - Routine	IRB ¹ and DSMC ² - Routine Review ³	IRB ¹ - Routine Review ³ DSMC ² -	IRB ¹ - Routine Review ³ DSMC ² - Within 5 calendar days	DSMC ² - Routine	DSMC ² - Heme : Routine review	DSMC ² - Within 5
Possible Probable Definite	Review ³	IRB ¹ and DSMC ² - Within 5 calendar days FDA ⁴ Sun Pharma ⁵	Within 5 calendar days	IRB ¹ and DSMC ² - Within 5 calendar days FDA ⁴ Sun Pharma ⁵	Review ³	Non- Heme: Within 5 calendar days	calendar days

- 1. Guidance on adverse event reporting to the IRB is available online at MCW IRB Policies and Procedures.
- 2. For expedited DSMC reporting, study coordinator/research nurse must notify the DSMC via email including the subject ID, date of event, grade, relatedness, expectedness, and a short narrative. DSMC will review data entered into OnCore®. Non-hematological grade 4, unexpected hematological grade 4 and all grade 5 events must be reported to the DSMC within five calendar days of study staff's knowledge. Expected hematological grade 4 adverse events will be routine reported.
- 3. For routine reporting, the events will be reported to IRB as part of the annual continuing progress report and the DSMC will review data entered into OnCore® at the time of scheduled monitoring.
- 4. Fatal or life-threatening SAEs meeting the criteria indicated in the above table will be reported to FDA no later than seven calendar days after study staff's initial awareness of the event. If the SAE is not fatal or life-threatening and meets the above criteria, the timeline for submitting an IND safety report to FDA is no later than 15 calendar days after study staff's initial awareness of the event. See section 7.2.2 for detailed reporting instructions.
- 5. Sun Pharmaceutical Industries Ltd. reporting requirements will be same as FDA (see footnote 4 above). For the purpose of reporting to Sun Pharmaceutical Industries Ltd, study staff should submit the MedWatch form and a deidentified OnCore® SAE report.

7.2.2 Reporting Instructions

Food and Drug Administration

An IND safety report will be submitted for any adverse event that meets all three definitions: possibly related to the study drug, unexpected and serious. If the adverse event does not meet one of the above definitions, it should not be submitted as an expedited IND safety report.

Any relevant additional information that pertains to a previously submitted IND safety report will be submitted to FDA as a Follow-up IND Safety Report without delay, as soon as the information is available (21 CFR 312.32(d)(2)).

Suggested Reporting Form:

US FDA MedWatch 3500A:

http://www.fda.gov/Safety/MedWatch/HowToReport/DownloadForms/default.htm

• Sun Pharmaceutical Industries Ltd. (Sponsor)

Serious adverse events (SAEs) as per the table above must be reported to Sun Pharmaceutical Industries Ltd.'s local safety representative by FAX at [contact] (preferred) or by email: [contact].

7.3 Unanticipated Problem Involving Risk to Subject or Other (UPIRSO)

The investigator and his or her team will follow the Medical College of Wisconsin policies related to unanticipated problems involving risks to subjects or others. This information may be found on the Human Research Protection Program website.

7.4 Reporting of Pregnancy

Female subjects who become pregnant during treatment and 30 days post the last dose of the study drug should discontinue the study treatment immediately. Study staff should report the pregnancy in OnCore® as a grade 3 SAE and email the PDF report to the study PI and DSMC coordinator within 24 hours of staff awareness.

If a male subject impregnates his partner during treatment and 30 days post last dose of the study drug, the study team should report the pregnancy in OnCore® as a grade 3 SAE and email the pdf report to the study PI and DSMC coordinator within 24 hours of staff awareness.

Whenever possible, a pregnancy (for either a subject or male subject's partner as described above and according to IRB policies regarding consent of this partner) should be followed to term, any premature termination reported, and the status of the mother and child should be reported. Data on fetal outcome and breastfeeding are to be collected for regulatory reporting and drug safety evaluation.

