Investigator/Enrolling Physician Initials:_____

Subject Initials:	Subject Study ID:	Enrolling Physician

- b. If subject is of childbearing potential (defined as not satisfying either of the above two criteria), she must agree to practice two acceptable methods of contraception (combination methods require use of two of the following: diaphragm with spermicide, cervical cap with spermicide, contraceptive sponge, male or female condom, hormonal contraceptive) from the time of signing of the informed consent form through 90 days after the last dose of study agent, **OR**
- c. Agrees to practice true abstinence when this is in line with the preferred and usual lifestyle of the subject. (Periodic abstinence [e.g., calendar, ovulation, symptothermal, post ovulation methods] and withdrawal are not acceptable contraception methods.)
- 11. Male subjects, even if surgically sterilized (i.e., status postvasectomy), must agree to one of the following:
 - a. Practice effective barrier contraception during the entire study period and through 60 calendar days after the last dose of study agent, **OR**
 - b. Agree to practice true abstinence when this is in line with the preferred and usual lifestyle of the subject. (Periodic abstinence [e.g., calendar, ovulation, symptothermal, post ovulation methods] and withdrawal are not acceptable methods of contraception.)
- 12. Signed informed consent: Voluntary written consent must be given before patient registration and performance of any study-related procedure not part of standard medical care, with the understanding that consent may be withdrawn by the patient at any time without prejudice to future medical care.
- 13. Planned post-transplant maintenance therapy is allowed.
- 14. Prior autologous transplant is allowed.

Exclusion Criteria

- 1. Prior allogeneic HCT.
- 2. Active CNS involvement with malignancy.
- 3. Patients receiving cord blood or haploidentical allograft.
- 4. Patients undergoing in vivo or ex vivo T cell-depleted alloHCT.
- 5. Karnofsky performance score <60% or ECOG > or = 2.
- 6. Patients with uncontrolled bacterial, viral or fungal infections (currently on treatment and with progression of infectious disease or no clinical improvement) at time of enrollment.
- 7. Active hepatitis B or C virus infection or known human immunodeficiency virus (HIV) positive.

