8 PHARMACEUTICAL INFORMATION

Tildrakizumab

- **8.1 Agent Description:** Tildrakizumab is a high affinity (297 pM), humanized immunoglobulin G1/kappa ($IgG1/\kappa$) antibody that specifically binds and neutralizes human IL-23 (SN 08197 [Addendum 1]). This antibody has been shown in Phase 1, Phase 2, and Phase 3 studies to reduce the clinical signs and symptoms of psoriasis.
- **8.2 Absorption:** Absolute bioavailability is 73–80% with slow absorption with time to reach maximum concentration at 6.2 days after SC injection. Tildrakizumab exposure increased

proportionally with dose and did not exhibit time-dependent PK. Steady-state is achieved by 16 weeks with the clinical regimen (dosing on Week 0 and Week 4 and Q12W thereafter) with 1.1fold accumulation in C_{max} . Tildrakizumab has low to moderate PK variability (33-41% CV).

- 8.3 Distribution: Tildrakizumab has limited extravascular distribution with an apparent volume of distribution (Vd/F) of 10.8 L, which was found to depend on the body weight. Plasma protein binding is not expected to impact tildrakizumab exposure.
- **8.4 Metabolism:** Tildrakizumab is catabolized by general protein degradation processes; typical small-molecule metabolic pathways (e.g., CYPs), glucuronosyltransferases) do not contribute to its clearance.
- **8.5 Elimination:** Tildrakizumab is catabolized into component amino acids by general protein degradation processes and is not eliminated by renal or hepatic pathways. Apparent clearance is independent of dose. Apparent elimination half-life (%CV) is 23.4 days (23%).
- **8.6 Contraindications:** As tildrakizumab is eliminated by protein catabolism, not affected by hepatic drug metabolizing enzymes and not eliminated by renal or hepatic pathways, no dose adjustments for tildrakizumab are necessary when co-administered with other therapies.
- 8.7 Side Effects: Complete and updated adverse event information is available in the Investigational Drug Brochure and/or product package insert.
- 8.8 Storage Requirements and Stability: Ongoing stability studies have shown that tildrakizumab solution DP in PFS is stable under refrigerated storage conditions (2°C to 8°C). Please refer to the package insert for additional storage and stability information.
- 8.9 Agent Destruction and Return: Used, and any unused study drug will be destroyed and documented, as per institutional standards.

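### Pregnancy reporting stops 30 days after the last dose, although the protocol's own contraception requirement runs to 90 days in women and at least 60 days in men

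*Combined protocol and SAP*

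**What the plan says.** Section 7.4 sets its rule for "Female subjects who become pregnant during treatment and 30 days post the last dose of the study drug". For men it applies "If a male subject impregnates his partner during treatment and 30 days post last dose of the study drug". Staff record each such pregnancy as a grade 3 serious adverse event. Where possible they follow it to term and collect fetal outcome. That follow-up refers back to the pregnancies just described, so it carries the same 30-day limit.

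Section 7.1.2 lists pregnancy among the outcomes that make an event serious. Section 7.2.1 has serious adverse events reported from consent "through 30 days post last dose of study drug(s) will be reported". Section 7.2 gives the same end point for adverse event collection in general.

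Section 4.5, criterion 10, requires women of childbearing potential who do not practise true abstinence to use two contraceptive methods "from the time of signing of the informed consent form through 90 days after the last dose of study agent". Criterion 11 gives men the choice of true abstinence or the following: "Practice effective barrier contraception during the entire study period and through 60 calendar days after the last dose of study agent". The Protocol Summary repeats both periods. No reason is given for the difference between these periods and the 30-day limit.

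**The concern.** The protocol considers it worth preventing conception for two to three months after dosing, yet requires staff to report a conception only in the first of those months. A pregnancy in the remaining time falls inside the contraception period but outside every reporting clause, including the clause on fetal outcome.

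Section 7.4 says fetal data are collected for regulatory reporting and drug safety evaluation, and the medication guide in Appendix 3 says it is not known whether the drug can harm an unborn baby. Each such pregnancy would be informative, and the plan does not require anyone to record it. No efficacy endpoint, analysis or stopping boundary is affected.

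**Working it through.** There is no figure in the plan to reproduce. The check is day arithmetic on these inputs:

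- Reporting limit: 30 days after the last dose (7.4, 7.2.1).
- Contraception limit W: 90 days in women, 60 days in men (4.5).
- Dosing days: −1, 28, 112, 196 and 280 (3.2).
- On treatment: from first to last dose (4.1), so the intervals between doses are covered by 7.4.
- Half-life: 23.4 days (8.5). Section 3.3 gives 21 to 24 days.

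**Share of the post-dose window not covered** = (W − 30) / W.

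- Women: (90 − 30) / 90 = 60/90 = 66.7%.
- Men: (60 − 30) / 60 = 30/60 = 50.0%.

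**Share of all days from first dose not covered** = (W − 30) / (days from first to last dose + W). With last dose on day d, the days from first to last dose are d + 1.

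| Last dose received | Women | Men |
|---|---|---|
| Day −1 | 60/90 = 66.7% | 30/60 = 50.0% |
| Day 28 | 60/119 = 50.4% | 30/89 = 33.7% |
| Day 112 | 60/203 = 29.6% | 30/173 = 17.3% |
| Day 196 | 60/287 = 20.9% | 30/257 = 11.7% |
| Day 280 | 60/371 = 16.2% | 30/341 = 8.8% |

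The full course is the smallest case. Sections 4.6 and 6.1 end dosing for relapse or progression needing treatment, grade III–IV acute GVHD and chronic GVHD needing systemic therapy. These are close to the non-fatal components of the primary endpoint, for which section 10.2.1 uses 20% as the historical 12-month event-free probability and 35% as the main alternative. Some of those events will come after the last dose or be deaths, so the number stopping early cannot be derived, but the upper rows are not rare exceptions.

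**Drug remaining t days after the last dose** = 0.5^(t / half-life), assuming simple first-order decline from the day of dosing.

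- Day 30: 0.5^(30/23.4) = 41% (37% to 42% for half-lives of 21 to 24 days).
- Day 60: 0.5^(60/23.4) = 17% (14% to 18%).
- Day 90: 0.5^(90/23.4) = 7% (5% to 7%).

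These fractions describe the treated subject only.

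**Men who stop early.** Criterion 11 also covers the entire study period. If that means 12 months after transplant, a man whose only dose was on day −1 has reporting to day 29 and contraception to day 365, a gap of 365 − 29 = 336 days. If only the 60-day clause governs, the gap is 30 days.

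**The case against.** The strongest objection is to a reading of the mismatch as meaning that most at-risk pregnancies would go unreported. The documents do not support that. Section 7.4 covers the whole treatment period, so for a full course about 84% of days in women and 91% in men are covered. The uncovered share exceeds half only in women, and only on the post-dose window alone or after one dose or, barely, two. In men it does not exceed half on the 60-day period. These are also shares of days; no conception rate is given, so they cannot be turned into shares of pregnancies.

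Two further inferences fail. The plan never calls the contraception period a risk window, and a precautionary contraception period can legitimately differ from a reporting period. Nor does a late pregnancy show that the contraception rule was broken, since compliant contraception can fail.

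It can also be said that such pregnancies would come to light anyway. The study calendar has an adverse event assessment at 12 months, each assessment reviews the whole period, and patients who stop dosing stay in follow-up (4.6, 6.6). This has some force: a day-365 visit falls 85 days after a day-280 dose. But with the stated windows (dose day 266 to 294, visit day 335 to 395) the interval runs from 335 − 294 = 41 to 395 − 266 = 129 days. More importantly, the calendar does not override the 30-day limits in 7.2, 7.2.1 and 7.4, and it does not require fetal outcome to be collected. It offers a chance to hear of a pregnancy, without a duty to report it.

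Finally, the residual-drug figures give no support for the male-partner window, because the documents contain nothing on transfer of drug through the father. That stands. For men the point rests only on the difference between the two stated periods.

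**Conclusion.** The gap is real and minor. Reporting and outcome follow-up end at 30 days, while the protocol's own contraception periods continue for a further 60 days in women and at least 30 in men, and no other section closes the difference. It is better described as a gap in safety capture than as a strict contradiction, because the two kinds of period need not be equal; but they differ without explanation, and the shorter one governs the data.

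The size rests on nominal dosing days and on taking the contraception period as the natural comparison, which is my inference. That few pregnancies will occur after myeloablative conditioning is an assumption, since the documents give no rate. I take no view on how long contraception should last.

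**What to change.** Reconcile sections 4.5, 7.2.1 and 7.4. The simplest way is to state in 7.4 a reporting and outcome follow-up window for pregnancies only, equal to the contraception periods already in 4.5, and to add a pregnancy exception to the 30-day limit in 7.2.1. If the sponsor has a reason for the shorter window, 7.4 should give it.

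Three details need care:

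- The first sentence of 7.4 also carries an instruction to discontinue treatment. Put the reporting window in a separate sentence so that the instruction is untouched.
- Word the exception so that it does not lengthen general adverse event or serious adverse event collection.
- State what the entire study period means in criterion 11. Section 6.6 follows patients for 12 months in total, while the study schema shows 12 months after the last dose. Day 280 + 90 = day 370, just beyond day 365, so those two passages must be reconciled for the window to be workable.

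The cost is a sentence in 7.4, a line in 7.2.1, and a small amount of extra reporting and follow-up for any pregnancy that occurs. Some patients may need a contact after the 12-month visit to reach the end of the window.

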7.5 Subject Complaints

If a complaint is received by anyone on the study staff, it will be discussed with the study staff and will be addressed on a case-by-case basis. The PI will be notified of any complaints. Complaints will be reported to the IRB if indicated.

If the subject has questions about his or her rights as a study subject, wants to report any problems or complaints, obtain information about the study or offer input, the subject can call the Medical College of Wisconsin/Froedtert Hospital research subject advocate at [contact]. This information is provided to the subject in their consent.

A product complaint is a verbal, written or electronic expression that implies dissatisfaction regarding the identity, strength, purity, quality or stability of a drug product. Individuals who identify a potential product complaint situation should immediately contact the drug manufacturer and report the event. Whenever possible, the associated product should be maintained in accordance with the label instructions pending further guidance from a drug manufacturer representative.

MCW Protocol No: PRO00035737 41 Version No. 7 Product complaints in and of themselves are not reportable events. If a product complaint results in an SAE, an SAE form should be completed.

